# I. Hypotheses and Specific Aims

The central hypothesis is that inhibitory insular TMS can be used to provide a non-invasive intervention to decrease nicotine craving, alter resting state brain connectivity, and reduce craving-associated insular activity in smokers. All experiments will be conducted in treatment-seeking smokers. These experiments are designed to evaluate the efficacy of insular neuromodulation using rTMS. Outcome measures include (1) cigarette craving measures, (2) resting-state fMRI connectivity measures, and (3) tasked-based fMRI insular activity measures. In a double-blinded two-arm (sham rTMS and inhibitory insular rTMS) randomized control trial with 20 smokers assigned to each arm, we will collect craving measurements, resting state fMRI, and task-based fMRI before and after a single session of rTMS treatment to investigate the following aims:

# AIM 1. Determine if insular rTMS reduces cigarette craving.

H1 Compared to sham, insular rTMS will reduce craving in response to cigarette cues.

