# IV. Research Methods

**A. Outcome Measure(s):** Outcome measures will include (1) cigarette craving measures, (2) resting-state fMRI connectivity measures, and (3) tasked-based fMRI insular activity measures.

A.1 Neuropsychological Testing: Our primary cognitive outcome will be the change after treatment compared to before treatment in the Questionnaire of Smoking Urges – Brief Version (QSU-brief), a measures craving. An additional important question is whether craving, smoking history, smoking characteristics, or personality traits are associated with specific changes in connectivity after treatment. Thus, we will perform the following assessments prior to treatment: (1) smoking history questionnaire, (2) Fagerstrom nicotine dependence scale (FNDS), (3) Wisconsin inventory of smoking dependence motives (WISDM-68), (4) behavioral inhibitory scale and behavioral activation scale (BIS/BAS), (5) Barratt impulsiveness scale (BIS-11). The QSU-brief will be administered before and after treatment. A visual analog scale will be used to quickly assess subjects' craving during the craving visual-cue task:

The craving data before and after treatment will be used to investigate Aim #1.

A.2. Magnetic Resonance Imaging. All MRI scans will be acquired using a 3.0 T Seimens Skyra MR system using a 20-channel head-neck coil. High-resolution 3D T1-weighted scans will be acquired before treatment for image registration and normalization. T2\* weighted echo-planar imaging blood oxygen level dependent fMRI will be acquired with 3.4 x 3.4 x 3.4 mm voxels, TR 2100 ms, TE 30 ms, and flip angle 70°. Two fMRI sequences will be acquired before and after treatment: (1) a 10 minute RS-fMRI, in which subjects will be asked to lie quietly in the scanner and not think of anything in particular; and, (2) a 15 minute task-based fMRI exam during a cigarette craving cue task. fMRI data will be processed and analyzed as described in the methods section (see C.4 through C.8). Briefly, outcome measures will include insular functional connectivity (see **Aim #3**) changes at the whole brain level after treatment compared to before treatment.

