#### C. Study Design and Research Methods

#### **Experimental Method for all Aims:**

C.1 Enrollment. Prior to informed consent, the inclusion and exclusion criteria will be reviewed with each subject. Once eligibility has been determined, each subject will be provided with verbal and written informed consent. All questions will be answered.

Each subject will participate in a single session, during which inclusion and exclusion criteria will be reviewed, the subject will provide informed consent, women will be have urine pregnancy screens, urine and breath drug and alcohol tests will be administered, standardized psychological assessments will be performed, and then resting and task-based fMRI scans before and after rTMS. The following is the projected timeline for a given subject's study appointment:

Stud	y Appointment Component	Duration (min)		
1.	Review of inclusion and exclusion criteria	10		
2.	Informed Consent	15		
3.	Urine and breath tests	5		
4.	Pre-treatment neurological examination	10		
5. Initial standardized surveys				
6. Pre-treatment MRI examination 49				
	High- definition structural T1W sequence	6		
	Resting-state fMRI sequence	10		
	Craving-cue task fMRI sequence/task	15		
	Magnetic Resonance Spectroscopy (MRS)	18		
7.	Walk to TMS Laboratory	5		
8.	rTMS Treatment	31		
9.	Walk to Brain Imaging Center	5		
10.	Post-treatment MRI examination	43		
	Resting-state fMRI sequence	10		
	Craving-cue task fMRI sequence/task	15		
	Magnetic Resonance Spectroscopy (MRS)	18		
11. Post-treatment QSU-Brief 2				
12.	Post-treatment neurological examination	10		
	Total:	205		

Subjects will be asked to remain abstinent from smoking for 3 hours prior to the study. Subjects will provide urine samples to screen for recent drug use and quantify urine cotinine levels. To ensure abstinence they must fill a questionnaire, test negative for alcohol by a breath screening test, and have a breath CO<10pp. Clinical assessment including a brief medical and psychiatric interview will be performed by [name] to determine eligibility. Subjects will undergo a brief (10 minute) neurological examination. Subjects will be educated on TMS and MR safety and will demonstrate their understanding.

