C.2 Demographic. Psychological, Smoking, and Craving Assessments: Subjects will complete a basic demographic survey to document the date of birth, sex, ethnicity, education, handedness, and use of glasses. Age and sex must be determined because gray matter characteristics and brain function vary by age. Education and handedness must be documented because brain function is affected by these variables. The use of glasses must be documented because if subjects are unable to see the images during the craving cue task, it can introduce a bias in the data.

Medical history, current medications, and surgical/procedural history will be documented. [name] will review this information to ensure that the subject meets no exclusion criteria, and to ensure that the subject is taking no medications that lower the seizure threshold.

Subjects will complete a brief smoking history questionnaire. This will characterize the severity and nature of the subject's cigarette dependence, which may affect their responses to craving cues.

Subjects will complete the Fagerstrom Nicotine Dependence Scale (FNDS). This is a valid and reliable standardized survey to quantify the degree of cigarette dependence.

Subjects will complete the Wisconsin Inventory of Smoking Dependence Motives (WISDM-68). This is a valid and reliable 68-item standardized survey designed to characterize the psychological constructs that motive an individual subject's smoking behaviors.

Subjects will complete the Questionnaire on Smoking Urges – Brief (QSU-Brief). This is a valid and reliable standardized survey to quantify a subject's current intensity of craving. This is the only standardized survey that in addition to being administered prior to rTMS treatment will also be administered after rTMS treatment.

Subjects will complete the Behavioral Inhibition Scale and Behavioral Activation Scale (BIS/BAS). The Behavioral Inhibition and Activation Scale is a 20-item self-reported questionnaire

used to measure responsiveness of motivational systems. The first component is the Behavioral Inhibition Scale, which is used to quantify avoidance behaviors and reactions to the anticipation of punishment. The second component is the Behavioral Activation Scale, which is used to quantify positive affective and approach response tendencies to appetitive stimuli.

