creates sound, vibrations, and electrical stimulation similar to the active coil. Subjects will undergo a brief (10 minute) neurological examination by [name] before and after rTMS treatment, which will include examination of the motor, sensory, language, abstract-thinking, memory, and spatial reasoning systems.

The specific parameters of the rTMS proposed in this study are as follows:

Parameter	Value
Manufacturer	MagnaStim
Model Name	Rapid2
510(k) or Master File Number	
Amplitude (% of motor threshold)	90%
Frequency (pulses per second) [a]	1 Hz

Train duration [b]	1500 sec (25 min)
Number of trains per session [c]	1
Number of sessions in study [d]	1
Cumulative exposure (total # of pulses = $a \times b \times c \times d$ )	1500 pulses
Intertrain interval (time between trains)	N/A

The following table is the maximum safe duration (in seconds) of a single train of rTMS, reproduced without permission from Rossi et al. Here, safety was defined as absence of seizure, spread of excitation or afterdischarge of EMG activity. Numbers preceded by > are the longest duration tested. This table was presented by consensus. The parameters proposed in our study are highlighted in yellow and well within safe limits.

Erog (Hz)	Intensity (% of motor threshold)					
Fied (EZ)	90%	100%	110%	120%	130%	
1	>1800	>1800	>1800	>360	>50	
5	>10	>10	>10	>10	>10	
10	>5	>5	>5	4.2	2.9	
20	2.05	2.05	1.6	1.0	0.55	
25	1.28	1.28	0.84	0.4	0.24	

C.4 Comparison of craving responses to treatment: QSU and visual-analogue craving measures will be compared using a multivariate analysis of covariance (see C.4.1.1). These comparisons will provide results for **Aim #1**.

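### H1 concerns craving in response to cigarette cues, but the named primary outcome is the QSU-brief, given outside the cue task, and no stated test isolates the cue-task rating

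*Combined protocol and SAP*

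**What the plan says.** Section I, Aim 1, gives H1 as: "Compared to sham, insular rTMS will reduce craving in response to cigarette cues". The title of Aim 1 is broader and asks only whether insular rTMS reduces cigarette craving.

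Section IV.A.1 sets the outcome: "Our primary cognitive outcome will be the change after treatment compared to before treatment in the Questionnaire of Smoking Urges – Brief Version (QSU-brief"). C.2 says of that questionnaire: "This is a valid and reliable standardized survey to quantify a subject's current intensity of craving". In the C.1 timeline the initial surveys are step 5, before the pre-treatment MRI (step 6). The second reading is a separate line after the post-treatment MRI (step 10): "11. Post-treatment QSU-Brief 2".

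A.1 also describes a second craving measure: "A visual analog scale will be used to quickly assess subjects' craving during the craving visual-cue task". The cue task is one of the two scans covered by the A.2 statement "Two fMRI sequences will be acquired before and after treatment".

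On analysis, C.4 says "QSU and visual-analogue craving measures will be compared using a multivariate analysis of covariance" and that this gives the Aim 1 result. F.1.1 fits a multivariate linear model to craving measures before and after treatment, without naming the scales, with treatment and FTND as predictors. It lists Hotelling-Lawley tests of treatment by time, time and treatment. It states no test of the visual analog scale (VAS) alone, no univariate follow-up, and no contrast of ratings by cue type. The smoking-versus-neutral contrast in C.7 and F.3.1 is for fMRI only.

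**The concern.** H1 makes a claim about cue-elicited craving. The scale named as primary is not read during cue exposure, and the scale that is read then has no test of its own. If the joint test is significant, the report could say that H1 is supported when only the QSU-brief moved. If the two scales disagree, nothing in the plan says which one answers H1, so the choice would be made after the data are seen. H3 concerns insular activity associated with cigarette cues, so readers will naturally set the Aim 1 result beside it as its behavioural counterpart.

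**Working it through.** **1. Where the readings fall.** The listed components of the C.1 timeline, without the surveys, sum to 10 + 15 + 5 + 10 + 49 + 5 + 31 + 5 + 43 + 2 + 10 = 185 min. The stated total is 205, which leaves 20 min for the surveys. Taking the steps in the listed order:

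| Event | Minutes from start |
|---|---|
| Initial surveys, including QSU-brief | 40–60 |
| Pre-treatment cue task | 76–91 |
| rTMS block | 114–145 |
| Post-treatment cue task | 160–175 |
| Post-treatment MRS | 175–193 |
| Post-treatment QSU-brief | 193–195 |

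The baseline QSU-brief precedes every cue. The post-treatment QSU-brief starts 193 − 175 = 18 min after the last cue and 193 − 145 = 48 min after the rTMS block. Cue-task ratings would fall 15 to 30 min after that block. The protocol calls this a projected timeline, and the 31-min block contains a 25-min train, so these are planned and approximate times.

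**2. The plan's own power figures.** F.1.2 gives d = 3.0 (active) and 1.9 (sham), a difference of 1.1. A two-sample t-test at two-sided 0.05 with 80% power needs 14.002 per arm, rounded up to 15, as stated. With 10% loss there are 20 × 0.9 = 18 per arm, and the smallest detectable effect is 0.961 (stated: 0.962). Both figures reproduce. They are figures for one outcome and one t-test, not for the joint test in F.1.1.

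**3. What the joint test can distinguish.** With two scales at two times, the treatment-by-time test compares the arms on two change scores. Assumptions: unit SD, correlation ρ between the change scores, one covariate, n = 18 per arm. If only one scale shifts, by δ = 0.962:

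- D² = δ² / (1 − ρ²), the same whichever scale shifts
- λ = (n/2) × D² = 9 × 0.9254 / (1 − ρ²) = 8.33 / (1 − ρ²)
- degrees of freedom: 2 and 2n − 2 − 1 − 2 + 1 = 32

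| ρ (assumed) | λ | Power, VAS only moves | Power, QSU-brief only moves |
|---|---|---|---|
| 0 | 8.33 | 69% | 69% |
| 0.3 | 9.15 | 74% | 74% |
| 0.5 | 11.1 | 82% | 82% |
| 0.7 | 16.3 | 94% | 94% |

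The two power columns are identical by construction, so rejection carries no information about which scale changed. A single t-test at this effect size has 80% power.

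**4. What a separate VAS test would need.** The documents do not say which craving scale the cited effect sizes come from, so carrying d = 1.1 over to the VAS is an assumption.

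| | n per arm for 80% | Power at 15 | Power at 18 | Detectable d at 18 |
|---|---|---|---|---|
| One test at 0.05 | 15 | 83% | 89% | 0.961 |
| Each scale at 0.025 | 18 | 74% | 83% | 1.07 |

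**The case against.** The strongest reply is that Aim 1 is about craving in general. Its title, the central hypothesis in Section I, the F.1 heading and Section G all put the question that way, and the QSU-brief suits it. Only the H1 sentence is narrower. This stands. It means that the QSU-brief is a defensible primary outcome and that rewording H1 is a legitimate remedy. The documents do not support the stronger inference that the QSU-brief must be replaced: doing so would exchange the scale that C.2 describes as validated for a brief rating.

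The second reply is that the VAS is already analysed. That is correct. C.4 names it, so a reader who infers that it was left out of Aim 1 would be wrong. What remains is that it has no test of its own.

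Third, a reader might infer that pooling weakens the test. That depends on the correlation: for a change confined to one scale, the joint test falls below 80% at assumed correlations of 0 and 0.3 but not at 0.5 or 0.7.

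Fourth, C.9 regresses brain measures on craving and dependence measures without limiting craving to the QSU-brief. So it cannot be said that the planned brain-behaviour analysis uses the wrong scale.

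Finally, the post-treatment QSU-brief follows the cue task while the baseline reading does not, so its change mixes cue exposure with elapsed time. Both randomised arms share this. It blurs what the change means but gives no ground for inferring bias in the arm comparison.

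**Conclusion.** The point holds as a mismatch between H1 and the test that would decide it. As written, Aim 1 can show that some craving measure differed between arms. It cannot show that craving during cue exposure did, so H1 could be declared supported without such a change. This follows from the plan's text and needs no assumption about correlation.

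The 69% to 94% range does rest on assumptions: unit-SD change scores, 18 per arm, a shift of 0.962 on one scale, and correlations of 0 to 0.7. It illustrates the symmetry of the joint test and is not evidence of a general loss of power.

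Two facts about the VAS are not settled by the text. Collection before and after treatment is inferred from the task being run twice. Nothing visible says how often ratings are made or whether they follow each cue type; the A.1 sentence ends in a colon, and the item it introduced may have been lost from the text. A ready-made contrast of ratings by cue type therefore cannot be assumed.

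**What to change.** In C.4 and F.1.1, take one of two routes.

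- **Keep H1 as worded.** Pre-specify a separate active-versus-sham comparison of pre-to-post change in the cue-task VAS as the test that decides H1. Test QSU-brief change separately; it may remain primary for general craving under Aim 1. State the testing order or the alpha split.
- **Keep the QSU-brief as the deciding outcome.** Reword H1 and the Aim 1 conclusion to current smoking urge, and drop the reference to cues.

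For the first route, state in A.1 that VAS ratings are taken in both cue-task runs, and when. Use a smoking-minus-comparison contrast only if ratings follow both cue types. Before defining it, reconcile the comparison images: the C.7 task description has food-related images, while its modelling text has neutral stimuli.

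The cost is mainly wording. If d = 1.1 carries over to the VAS, one test at 0.05 still needs 15 per arm. Testing both scales at 0.025 lowers power from 83% to 74% at 15 per arm and from 89% to 83% at 18. A fixed order avoids this for the scale tested first, but the second can then be claimed only if the first succeeds. The choice should be fixed before unblinding.

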# AIM 2. Determine if insular rTMS alters insular connectivity.

H2 Compared to sham, insular rTMS will reduce fMRI connectivity between the insula and brain regions associated with executive control, reward, and habit formation.

#### AIM 3. Determine if insular rTMS alters insular activity.

H3 Compared to sham, insular rTMS will reduce fMRI insular activity associated with cigarette cues.

# II. Background and Significance

**Nicotine dependence is a major health problem:** Smoking is the single greatest preventable cause of mortality, morbidity, and unnecessary health care costs in the US. It is estimated to cause 443,595 deaths annually and \$193 billion per year in smoking-related health care costs and productivity losses. Globally, tobacco results in over 6 million annual deaths and over half a trillion dollars in economic damage.

**Current treatments of nicotine dependence are inadequate:** Nicotine dependence is notoriously difficult to treat, with relapse rates approximately 85% for counseling therapy and 78% for combined counseling and pharmacologic therapy. Long-term abstinence from smoking is uncommon, with 6 month abstinence rates ranging between 19% and 33%. High levels of craving have been repeatedly shown to be associated with high relapse rates. Development of novel therapies to target craving could dramatically improve abstinence rates, decrease healthcare costs, and prolong lives.

The insula plays a key role in nicotine dependence: The insula is involved in interoception and salience. It integrates external information about stimuli and internal sensations including cognitive, homeostatic, and emotional states, to guide behavior. The anterior insula has been shown to exhibit functional connectivity with the superior, middle, and inferior frontal gyri, bilateral temporoparietal junction, anterior cingulate cortex, precuneus, basal ganglia, nucleus accumbens, and thalamus. Directed information flow from the insula to other brain regions, visible by fMRI, is increased in abstinent compared to satiated states in heavy smokers. Moreover, the anterior insula shows increased connectivity during smoking cues compared to food cues with somatosensory cortex, amygdala, and basal ganglia, which increases as dependence severity increases. A large meta-analysis demonstrated correlation between anterior insular cue-reactivity and subjective craving. The anterior insula is also involved in aspects of nicotine dependence other than craving, such as delayed discounting, valence, and mitigating aversion to negative consequences of smoking.

Several lines of evidence suggest involvement of the anterior insula in maintenance of nicotine addiction. In a landmark study, Naqvi et al reported that smokers with cerebrovascular damage to the insula were able to stop smoking easily without cravings or relapse, supporting a role of the insula and a broader interoception circuit in addiction. A prospective study over a one-year timespan replicated the conclusion that insular lesions were strongly associated with smokers spontaneously becoming non-smokers. These findings have been corroborated in rat models of nicotine dependence. Insular inactivation significantly reduced nicotine motivation, nicotine seeking-, and nicotine taking-behaviors, with no effect on food behaviors. Results of bilateral insular deep brain stimulation lesions in animal models are also consistent with this hypothesis. Given this evidence, inhibiting the anterior insula may be a useful strategy to reduce cigarette craving, as will be studied in **Aim #1**.

Sutherland et al. recently proposed an elegant explanatory "toggle" hypothesis, applying the work by Seeley et al. to nicotine dependence. Briefly, the hypothesis centers upon the salience network, comprised of the insula and anterior cingulate cortex. The insula is believed to "toggle" this network, directing brain function towards endogenous (i.e., default mode network) or exogenous (i.e., executive control network) stimuli. This insular function becomes usurped in nicotine addiction. The concept that the insula directs consciousness towards the most homeostatically relevant stimuli – internal or external – provides a neurobiological model to explain the cognitive deficits and functional connectivity findings of acute nicotine ingestion, nicotine satiety in dependence, and nicotine withdrawal. It also provides a mechanism for the findings of spontaneous smoking cessation in patients with insular lesions. Importantly, the model affords the opportunity to investigate non-invasive perturbation of specific nodes (e.g., insular cortex) to reduce craving and hopefully improve abstinence rates. We plan to study this functional perturbation in **Aim #2** and **Aim #3**.

**Neuromodulation in nicotine dependence shows promising results:** Repetitive transcranial magnetic stimulation (rTMS) is a non-invasive neuromodulatory technique in which a pulsatile magnetic field is created using an external solenoid to induce targeted depolarization of cortical neurons via electromagnetic induction. High frequency rTMS (> 3 Hz) transiently increases cortical excitability, while low frequency rTMS (1 Hz) reduces it. TMS to the dorsolateral prefrontal cortex (DLPFC) has demonstrated good test-retest reliability in fMRI connectivity.

Several studies have reported that excitatory rTMS targeting the DLPFC reduces cigarette craving and cigarette consumption. Moreover, studies have demonstrated that a *single session* of excitatory DLPFC rTMS causes short-term reduction of cigarette craving, cigarette consumption, cocaine craving, and craving induced by appetitive food. These findings are consistent with the salience "toggling" hypothesis. Prefrontal cortex exerts top-down control to bias information in lower-level somatosensory cortices towards relevant input and guide goal-directed behavior. Enhancing prefrontal cortical activity through neuromodulation would be expected to shift the balance of neural circuitry away from the DMN and towards the ECN, biasing consciousness away from endogenous stimuli such as craving.

While previous work has reported that TMS targeting the dorsolateral prefrontal cortex (DLPFC) modulates craving responses; human stroke and animal model literature suggests that the

insula may be more important in "toggling" away from DMN and toward ECN. To date only one paper describes rTMS specifically targeting the insula: a study of seven patients, reporting subjective changes in cold perception and tolerance of the intervention. Dinur Klein et al. applied high-frequency, low-frequency, and sham rTMS to the bilateral DLPFC with some magnetic field spread into the anterior insulae bilaterally. They reported high-frequency bilateral stimulation significantly reduced cigarette consumption and nicotine dependence, with significantly increased levels of abstinence both immediately after the treatment and at 6 months follow-up. No fMRI data were obtained. The major weakness of the Dinur-Klein et al study is that it primarily targeted the DLPFC, with minimal excitatory posterior treatment coverage of the insula. Given the salience toggling hypothesis, to optimally modulate craving therapies one should provide either excitatory stimulation to the DLPFC or inhibitory stimulation of the insula. *While most experts in this field acknowledge the critical role of the insula in nicotine dependence, there has been surprisingly little research exploring neuromodulation of the insula as a potential therapy.* 

This proposal seeks to answer several questions: (1) Can inhibitory TMS be used to reduce cigarette craving in smokers? (2) Can inhibitory insular TMS alter insular connectivity and activity? And, (3) does inhibitory insular TMS alter brain-behavior relationships? The literature implicating the insula in maintenance of craving in smokers suggest rTMS targeting the insula may provide a more robust modulation of nicotine craving.

